## 7.2.2. Participant Discontinuation

Discontinuation is expected to be uncommon.

At the time of discontinuing from the study, if possible, an early discontinuation visit should be conducted, as shown in the SoA. See the SoA (Table 1.1) for data to be collected at the time of study discontinuation and follow-up and for any further evaluations that need to be completed. The participant will be permanently discontinued from both the study intervention and the study at that time.

If the participant withdraws consent for disclosure of future information, the Sponsor may retain and continue to use any data collected before such a withdrawal of consent.

Participants will be discontinued in the following circumstances:

- enrolment in any other clinical study involving an investigational product or enrolment in any other type of medical research judged not to be scientifically or medically compatible with this study
- participation in the study needs to be stopped for identified medical, safety, regulatory, or other reasons consistent with applicable laws and regulations
- a participant becomes pregnant during the course of the study
- the investigator decides that the participant should be discontinued from the study
- a participant did not meet the enrolment criteria and was inadvertently enrolled, and
- the participant, the participant's designee, for example, parents or legal guardian requests to be withdrawn from the study.

If the Sponsor or investigator identifies a participant who did not meet enrolment criteria and was inadvertently enrolled, then the participant should be discontinued from study treatment, unless there are extenuating circumstances that make it medically necessary for the participant to continue on study treatment.

If the Sponsor and the investigator agree that it is medically appropriate to continue, the investigator must obtain documented approval from the Sponsor to allow the inadvertently enrolled participant to continue in the study with or without treatment with study product.

## 7.2.3. Lost to Follow-Up

A participant will be considered lost to follow-up if he/she repeatedly fails to return for scheduled visits and is unable to be contacted by the study site.

Site personnel are expected to make diligent attempts to contact participants who fail to return for a scheduled visit or were otherwise unable to be followed up by the site.

## 8. Study Assessments and Procedures

Study procedures and their timing are summarised in the SoA (Table 1.1).

Immediate safety concerns should be discussed with the Sponsor immediately upon occurrence or awareness to determine if the participant should continue or discontinue study intervention.

Adherence to the study design requirements, including those specified in the SoA, is essential and required for study conduct.

All screening evaluations must be completed and reviewed to confirm that potential participants meet all eligibility criteria. The investigator will maintain a screening log to record details of all participants screened and to confirm eligibility or record reasons for screening failure, as applicable.

Table 1.1 lists the SoA, with the study procedures and their timing (including tolerance limits for timing).

#### 8.1. Effectiveness Assessments

## 8.1.1. Primary Assessments

The primary assessment compares the number of MBDs per week in Study Period 1 and Study Period 2 in participants with T1D or T2D using CGM measurements and CCl data. Missed bolus doses will be determined by the glucose excursion as measured by the CGM.

Missed bolus dose (Figure 8.1) is defined as no insulin dose from 1 hour prior to through 1 hour after the start of a glucose excursion (meal), where a glucose excursion was defined as a >70 mg/dL (>3.9 mmol/L) rise within 2 hours, not preceded by a value <70 mg/dL (<3.9 mmol/L) (Edwards et al. 2021).

[figure not shown]

Figure 8.1. Illustration of missed bolus dose and mistimed bolus.

Using Figure 8.1 as an example, in this study:

- if a dose between 10 and 11 am would be classified as the correct or optimum time to administer the insulin dose, no insulin dose between 10 am and 12 pm would be a MBD; and
- if a dose between 5 and 6 pm would be classified as the correct or optimum time to administer the insulin dose before the meal, an insulin dose between 6 and 7 pm is defined as a mistimed bolus dose.

Sy et al. (2022) provides a graphical representation of several days of CGM data with various meal bolus situations.

## 8.1.2. Secondary Assessments

Study IORW will have secondary measures as described in Table 3.1.

The study will evaluate the change in percentage TIR, TAR, TBR, mean sensor glucose coefficient of variation between Study Period 1 and Study Period 2 in participants with T1D or T2D using CGM and CCl data. The glucose TIR for this analysis is ≥70 and ≤180 mg/dL.

In addition, the occurrence and change in mistimed bolus will be evaluated (Figure 8.1). A mistimed bolus dose is defined as a bolus dose administered from the start of a glucose excursion (meal) up to 1 hour after the start of glucose excursion and before the peak of glucose excursion.

Change in correction boluses from masked to unmasked period will also be evaluated. Correction bolus is defined as taking a bolus dose given after the peak of a glucose excursion but within 4 hours from the start of a glucose excursion and prior to start of next glucose excursion.

## 8.1.3. Exploratory Assessments

Study IORW will also have exploratory assessments:

- Sensitivity analysis for calculation of MBDs, using CGM curves integrated with the data received from the Tempo Pen/Smart Button.
- Participant interaction with the RMA based on app usage data (e.g., number of connections to the app, number of CCI data uploads, percentage of CGM data available, percentage of CCI data available) and comparison of usage in Study Period 1 and Study Period 2.
- Change in HbA1c from baseline to Visit 7.
- Understanding changes in participant views on a connected diabetes management platform.
- Understanding changes in HCP views on a connected diabetes management platform.
- Understanding the participant's fear of hypoglycaemia and correlate it with MBD.
- Understanding and summarizing the participant's day and night time CGM profiles during the two periods.

## 8.2. Safety Assessments

Not applicable as no clinical laboratory test are planned for this study. However, if any laboratory tests need to be performed during routine care for participant safety evaluations, it will be the responsibility of the HCP.

#### 9. Statistical Considerations

## 9.1. Statistical Hypotheses

The primary objective of this single-arm study is to compare the number of MBDs during the masked and unmasked app periods in participants with T1D and T2D via the Tempo Pen with Tempo Smart Button and on CGM.

The primary analyses will be conducted at the end of the clinical study on data collected from all participants as described in the Sections 9.2 and 9.3.

## 9.2. Analyses Sets

Safety analyses will be carried out on the **Safety Population**, which consists of all participants with at least 1 measurement in the masked app period and/or unmasked app period.

Efficacy analyses will be carried out on the main analysis set. To allow for this clinical trial to be generalisable to the wider population and to prevent the chance of analysing a biased set of "only adherent" participants, efficacy analyses will be repeated on the sensitivity analysis set.

## 9.2.1. Main Analysis Set

The initial 4 weeks will allow a wider population of participants (Humalog and non-Humalog users as well as those using and not using Dexcom G6 CGM prior to study entry) to reach a routine before baseline data assessment (such as MBD, TIR, TAR, etc.) is carried out.

Unless stated otherwise, data collected from the last 2 weeks (Weeks 5 and 6) of the masked app (baseline) period and the last 4 weeks (Weeks 15 to 18) of the unmasked app period will be used to answer the primary and secondary objectives. In other words, 2 weeks prior to Visit 3 (face-to-face) and 4 weeks prior to Visit 7 (face-to-face).

Following the guidelines of the Advanced Technologies and Treatments for Diabetes (ATTD) consensus on CGM use, only participants with at least 10 days' worth of CGM data out of the last 14 days (Weeks 5 and 6) in the masked app period will be considered as evaluable participants (Danne et al. 2017; Battelino et al. 2023).

Among these participants (as described above), only the participants that satisfy the below criteria for the unmasked app period will be considered as evaluable participants:

- with at least 20 of 28 days' worth of CGM data (Weeks 15 to 18), or
- discontinuing early that have at least 20 days' worth of CGM data in the whole unmasked app period (Weeks 7 to 18).

## 9.2.2. Sensitivity Analysis Set

The sensitivity analysis set includes all participants in the main analysis set, plus participants with at least 10 days' worth of CGM data in the whole masked app period (Weeks 1 to 6), and all participants with at least 20 days' worth of CGM data in the whole unmasked app period (Weeks 7 to 18).

## 9.3. Statistical Analyses

Statistical analysis of this study will be the responsibility of Lilly or its designee. Efficacy analyses will be conducted on the main and sensitivity analysis sets and safety analyses on the safety analysis set, unless stated otherwise.

The analyses for the primary endpoint and majority of the secondary endpoints (TIR, TAR, TBR, mistimed bolus, correction bolus) will be conducted using a mixed-effect models for repeated measures which will:

allow the model to adjust for key baseline characteristics (baseline HbA1c and body mass index) if appropriate, and

compare the masked app period against the unmasked app period.

Spearman rank-order correlation will be used to test the association between MBD and:

- TIR
- TAR
- TBR, and
- HbA1c.

For all statistical tests,  $p \le 0.05$  is considered statistically significant. No multiplicity adjustment will take place.

For continuous variables, descriptive statistics will entail:

- mean
- standard deviation (SD)
- minimum
- median, and
- maximum.

For categorical variables, frequency, and percentage will be obtained.

Baseline characteristics (such as type of diabetes, gender, age, duration of disease, etc.) will be summarised for all the participants entered in the trial, and for the analysis sets described above.

Where appropriate, graphs to illustrate glucose levels will be also be presented.

Amount of useable data from the CGM device and pen will be summarised for the main analysis set. The primary reasons for discontinuation will be summarised by Study Period and participant allocation will be summarised by investigative site for those who have entered the trial.

Any change to the data analysis methods described in the protocol will require an amendment ONLY if it changes a principal feature of the protocol. Any other change to the data analysis methods described in the protocol, and the justification for making the change, will be described in the clinical study report (CSR). Additional exploratory analyses of the data will be conducted, as deemed appropriate.

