#### 2.4.1. Clinical Benefit

With the aid of methods and devices used in this study, some participants may improve glycaemic control as a result of:

- reduction of MBDs
- ability to reliably and objectively track and view data on insulin dosing CCl and CGM leading to more accurate insulin dose adjustments and disease understanding during unmasked Study Period
- availability of other tracking features in Glooko RMA, and
- more interactions with HCP via regular remote visits during the trial period engaging in productive conversations based on reliable, objective data to better manage the disease.

The results of this study will:

- offer valuable insights into the potential advantages of the connected devices in insulin treatment and diabetes management, and
- provide further and more reliable clinical evidence to confirm what was observed in Adolfsson et al. (2020) study, focusing on showing a reduction of MBDs, and potential improvement in TIR, for patients with T1D as well as T2D on basal bolus therapy.

In addition, the objective collection of bolus dosing data CCI will help to better understand actual dosing behaviour in relation to the assessment of interstitial glucose values measured by the commercially available CGM device used by the person. The completion of participant behaviour and satisfaction questionnaires will help to better understand user behaviour for daily diabetes management (timing of insulin injection, missing bolus, etc.) and its relationship with bolus dosing.

As a result, it is anticipated that the productive conversations between the study participant and HCP, based on the data generated by the connected study platform, may result in a reduction of MBDs and improvement in participant's own diabetes management.

More detailed information about the known and expected benefits and risks and reasonably expected adverse events (AEs) of using a connected insulin management platform may be found in the Investigator's Brochure.

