## 9.3.2. Secondary Endpoints

The following endpoints will be calculated and analysed with the model described in Section 9.3 for the masked and unmasked periods:

- Change in participant CGM TIR ( $\geq$ 70 and  $\leq$ 180 mg/dL).
- Change in participant CGM TAR (>180 mg/dL and >250 mg/dL).
- Change in participant CGM TBR (<54 mg/dL and  $54 \text{ mg/dL} \le X < 70 \text{ mg/dL}$ ).
- Change in mistimed bolus dose [0,1] administering a bolus dose from the start of a glucose excursion to 1 hour after the start of glucose excursion and before the peak of the glucose excursion, is classified as a mistimed bolus dose. The definition of a glucose excursion remains the same for an MBD.
- Change in correction boluses taking a bolus dose after the peak of a glucose excursion but within 4 hours from the start of a glucose excursion and prior to start of next glucose excursion.
- Change in insulin doses: basal and mealtime, ratio basal/mealtime, dose per meal as well and total dose in IU/kg.
- Correlations between MBD/mistimed bolus and:
  - o TIR
  - o TAR
  - o TBR, and
  - o HbA1c.
- Other secondary analyses:
  - o evaluate coefficient of variation (from CGM data)
  - o evaluate mean sensor glucose (from CGM data).
- Exploratory analyses:
  - o change in HbA1c from baseline (Visit 1) to Visit 7 (last visit),
  - o healthcare professional questionnaires, and
  - o participant questionnaires
  - o day and night time CGM profiles during the two periods.

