## 9.4. Sample Size Determination

This clinical study aims to enroll approximately 50 participants (i.e., with signed informed consent and meeting all eligibility criteria) in sites across France. This sample size provides ≥80% power to detect a mean difference of daily MBD of 0.323 between the unmasked and masked RMA periods.

The sample size also assumes:

- a conservative correlation estimate of 0.2 between the unmasked and masked RMA periods
- an SD of 0.419 for the mean difference, and
- a 2-sided alpha of <0.05 (Adolfsson et al. 2020).

The estimated mean difference of 0.323 daily MBD is equivalent to a clinically relevant improvement of approximately 2.3 fewer MBD per week in the unmasked RMA period compared to the masked RMA period (also approximately 11% improvement).

As this is a relatively new field with very limited data, a range of correlations and standard deviations was considered in the sample size calculation as well as varying dropout rates. Table 9.1 provides an overview of how the appropriate sample size was identified.

Table 9.1. Sample Sizes of Evaluable Participants Needed to Detect at Least a Mean Difference of 0.323 Missed Bolus Doses Per Day (Alpha=0.05, Power=80%)

Correlation	Standard deviation (SD)			
	0.4	0.419	0.5	0.6
0.2	22	24*	33	46
0.3	19	21	29	40
0.4	17	18	25	35
0.5	15	16	21	30

\*Note: represents appropriate sample size identified for current study.

A sample size of approximately 50 participants will be sufficient to allow:

- at least 24 participants will complete the study with analysable data (see Table 9.1 and Section 9.2.1)
- scope for increased variability (up to SD of 0.5)
- for non-analysable participants due to technical problems
- 35% dropout rate was assumed based on previous study results (Adolfsson et al. 2020, Gomez-Peralta et al. 2022,) and the impact of missing CGM data which would reduce the number of evaluable patients.

Participants who are entered but who do not proceed to the unmasked stage will be discontinued from the final efficacy analysis and may be replaced to ensure that enough participants complete the study. Best effort will be made to recruit an approximate ratio of 4:1 for T1D and T2D (approximately 40 participants with T1D and 10 participants with T2D) in this clinical study. Withdrawals will be monitored to ensure there are enough participants with T2D enrolled.

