2.1. Multiplicity Adjustment

A p-value of \leq 0.05 will be considered statistically significant. No adjustments for multiplicity will take place.

3. Analysis Sets

For the purposes of analysis, the following analysis sets are defined:

Participant Analysis Set	Description			
Main Analysis Set	All continuous glucose monitoring (CGM) data should be included in the final analysis, but the proportion of participants who met the minimum 70% data-obtainment requirement during 14 days should be reported as part of the data completeness. Participants with ≥70% of CGM data present for a particular day will be considered complete for the day or valid CGM day. Similarly daytime and nighttime periods will be checked separately for valid CGM period. Following the guidelines of the Advanced Technologies and Treatments for Diabetes (ATTD) consensus on CGM use, only participants with at least 10 days' worth of valid CGM data out of the last 14 days (Weeks 5 and 6) in the masked application period will be considered for the main analysis set (Danne et al. 2017; Battelino et al. 2023).			
	Among these participants, only participants that satisfy the below criteria for the unmasked application period will be considered as evaluable participants and included in the main analysis set:			
	 participants with at least 20 of 28 days' worth of CGM data (Weeks 15 to 18), or participants discontinuing early that have at least 20 days' worth of CGM data in the whole unmasked application period (Weeks 7 to 18). 			
	Efficacy analyses will be carried out on the main analysis set. To allow for this clinical trial to be generalizable to the wider population and to prevent the chance of analyzing a biased set of "only adherent" participants, efficacy analyses will be repeated on the sensitivity analysis set.			
Sensitivity Analysis Set	The sensitivity analysis set includes all participants in the main analysis set, plus participants with at least 10 days' worth of CGM data in the whole masked application period (Weeks 1 to 6), and all participants with at least 20 days' worth of CGM data in the whole unmasked application period (Weeks 7 to 18).			
Safety Analysis Set	Safety analyses will be carried out on the Safety Population, which consists of all participants with at least 1 measurement in the masked application period and/or unmasked application period.			

4. Statistical Analyses

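### About 24 to 28 secondary tests are all judged at p ≤ 0.05 with no order, adjustment or nominal label, so a secondary result could be reported as statistically significant even if the primary fails

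*Protocol*

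**What the plan says.** Protocol 9.3 sets one threshold for every test. A p-value of 0.05 or less counts as statistically significant, and the next sentence reads: "No multiplicity adjustment will take place". SAP 2.1 gives the same threshold and says "No adjustments for multiplicity will take place". Protocol 9.4 states the level for the primary comparison as "a 2-sided alpha of <0.05".

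There is one primary endpoint, the change in missed bolus doses (MBDs) per week, and SAP 2 writes a null hypothesis for that endpoint only. Protocol 9.3.2 and SAP 4.4 then send the secondary endpoints through the same repeated-measures model, with a between-period difference, confidence limits and a p-value. Spearman correlations are added. The secondary endpoints have no testing order, no gate on the primary and no statement that their p-values are nominal.

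The plan does mark other analyses as non-inferential. SAP 4.4.1.1.10 plans no formal testing of the questionnaires, and SAP 4.8.2 limits subgroups to summary statistics. The secondary endpoints carry no such mark.

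On expected benefits, Protocol 2.4.1 describes the study as "focusing on showing a reduction of MBDs, and potential improvement in TIR".

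**The concern.** One rule covers the primary comparison and two dozen or more secondary tests. As written, it lets any secondary p-value at or below 0.05 be reported as statistically significant, including after a non-significant primary result. The study is open-label and single-arm, and plans for at least 24 evaluable participants (about 32 if 35% of 50 are lost).

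TIR is listed first among the secondary endpoints and is named in the benefit section, so it is the likeliest to be quoted. Under the rule it is one of more than 20 tests with no joint error control, and a reader of the results could not tell how much weight its p-value should bear.

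**Working it through.** **1. The plan's own figure.** The documents give no error rate for the secondary family. The nearest stated figure is the primary's 24 evaluable participants (Protocol 9.4, Table 9.1). Taking 0.419 as the per-period SD, which is the reading under which Table 9.1 reproduces, the SD of the difference is 0.419 × √(2 × (1 − 0.2)) = 0.530. A paired t-test for a difference of 0.323 at two-sided 0.05 and 80% power then needs n = 24, as stated. The calculation treats the primary as a single 5% test, so relabelling the secondary tests does not alter it.

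**2. Count of secondary tests** (Protocol 9.3.2; SAP 4.4.1.1.1 to 4.4.1.1.9)

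- Glycaemic models, 7: "Change in participant CGM TIR" (1); "Change in participant CGM TAR (>180 mg/dL and >250 mg/dL" (2); time below range in two bands (2); coefficient of variation (1); mean sensor glucose (1).
- Bolus models, 2: mistimed and correction boluses.
- Insulin-dose models, 7: basal, mealtime, their ratio, total, and breakfast, lunch and dinner.
- Spearman correlations: missed and mistimed boluses, each against TIR, time above range (TAR), time below range (TBR) and HbA1c. That is 2 × 4 = 8, or 2 × 6 = 12 if TAR and TBR are each split by threshold.

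Total: 9 + 7 + 8 = 24, to 9 + 7 + 12 = 28. A snack-dose model would make 29. Exploratory tests are left out. So are repeats on the sensitivity set, on which the documents differ: Protocol 9.2 and SAP 4.1 repeat the efficacy analyses there, while SAP 4.4 places the secondary analyses in the main set.

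**3. Any false positive, all secondary nulls true**

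- Expected number, whatever the correlation: 24 × 0.05 = 1.2; 28 × 0.05 = 1.4.
- At least one, independent tests: 1 − 0.95^24 = 70.8%; 1 − 0.95^28 = 76.2%. For jointly normal test statistics and two-sided tests, correlation can only lower this, so it is an upper bound.
- At least one, correlated tests, by simulation with normal test statistics. The correlations are assumptions.

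| Assumed correlation | Same between all pairs, 24 / 28 tests | Within five blocks only, 24 / 28 tests |
|---|---|---|
| 0.3 | 60% / 64% | 67% / 72% |
| 0.5 | 46% / 49% | 61% / 66% |
| 0.7 | 31% / 33% | 53% / 57% |

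The blocks are glycaemic (7), bolus (2), insulin dose (7) and the two sets of correlations (4 or 6 each). At a within-block correlation of 0.9 the figures fall to 40% / 42%.

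**4. A false benefit.** Insulin-dose changes and correlations are not benefits. That leaves the nine glycaemic and bolus endpoints, counting fewer correction boluses as favourable. Only the favourable tail, 0.025 per test, matters.

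- Independent: 1 − 0.975^9 = 20.4%.
- Equal correlation of 0.5: 13.5%. Equal correlation of 0.7: 10.1%.
- Limit under any dependence: 9 × 0.025 = 22.5%.
- A single test: 2.5%.

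**The case against.** The case for leaving the plan alone is substantial. There is one primary endpoint, its error rate is not inflated by what follows, and the endpoints are already tiered as primary, secondary and exploratory. Both documents say openly that nothing is adjusted, so a careful reader can discount secondary p-values. The secondary model code already requests confidence limits. No document calls a secondary result confirmatory, and unadjusted secondary testing is common in small pragmatic studies.

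The calculation also has limits. TIR, TAR, TBR, mean glucose and the coefficient of variation come from one glucose trace. Total dose and the basal/mealtime ratio are built from the same components. Strong correlation is therefore to be expected, and 71% to 76% sits at the top of the range. A missed bolus is itself defined by a glucose rise on that trace, so a null of no association with TIR or TAR is doubtful. Setting all the correlations aside leaves 16 models, with 0.8 false positives expected and 1 − 0.95^16 = 56% if independent.

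Two stronger readings are tempting. A reader might infer that a spurious secondary benefit is more likely than not. The documents do not support that, because 15 to 19 of the tests are not benefit measures and a false benefit needs the favourable tail. A reader might also infer that the protocol commits itself to a TIR claim. Protocol 2.4.1 speaks only of a potential improvement, and Protocol 2.1.4 lists injection timing and dose adjustment among the aims as well.

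These points limit the size of the problem and make a TIR gate a matter of choice. They do not answer the labelling point. Disclosing that nothing is adjusted is different from saying that secondary p-values are nominal, and the current rule says the opposite: such results are statistically significant.

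**Conclusion.** The point holds as a cheap improvement in labelling and does not affect the validity of the primary test. The same threshold applies to about 24 to 28 secondary tests, with 1.2 to 1.4 false positives expected if every secondary null is true. The chance of at least one is at most 71% to 76% and about 31% to 72% under the assumed correlations of 0.3 to 0.7. The chance of a falsely favourable result on a benefit-type endpoint is about 10% to 20%, roughly four to eight times that of a single test.

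These figures rest on all secondary nulls being true, on correlations that the documents do not supply, and on the count in step 2 of the working. Any real effect on a secondary endpoint lowers them. The consequence that needs no such assumption is that the text permits a claim of statistical significance for TIR, or any other secondary endpoint, after a failed primary.

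**What to change.** Replace the multiplicity sentence in Protocol 9.3 and in SAP 2.1, and align the threshold sentence beside it, with text such as:

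*Only the primary comparison is tested for statistical significance, at two-sided 5%. Secondary and exploratory p-values are nominal, are reported with 95% confidence intervals, and are not described as statistically significant.*

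Optionally, if the sponsor wants a formal claim on TIR, add that TIR is tested at two-sided 5% only after a significant primary result (fixed sequence). This leaves the primary at its full 5% and gives TIR a full 5% test when the primary succeeds.

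The cost is one or two sentences per document, with no loss of power for the primary and no extra participants. The downside is that fewer secondary results may be called significant. The change should be made before database lock. SAP version 1 is based on the protocol dated 29 June 2023, which has since been amended, so an SAP update is a natural place for it. By Protocol 9.3's own rule, a protocol amendment is needed only if the change alters a principal feature; otherwise the change and its reason go in the clinical study report.
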